## Kranus Health GmbH\_DINKS

Statistical methods:	
The primary endpoint (1) relative change rel-CfB-IEF week 12 regarding baseline of incontinence episodes is analysed using an analysis of covariance with the baseline value of the IEF as covariate and the factor treatment; the significance level is 5% 2-sided. Endpoint (2) change in the ICIQ-SF questionnaire, endpoint (3) change in quality of life in the I-QOL questionnaire and endpoint (4), change in PAM-13, are tested analogously with an ANCOVA at the 5% 2-sided level; to control for multiplicity, the analyses of endpoints (1) - (4) are tested sequentially using the method of a priori ordered hypotheses.
 
The other endpoints are analysed descriptively with p-values and 95% CIs.

Financing/Sponsor:	Kranus Health GmbH

Kranus Health GmbH\_DINKS

1.5 Business round scheme

Table 1: Visit scheme for the DINKS study

	Study implementation / treatment phase							Follow Up			
	Before enrolment/ pre-screening	Inclusion	Baseline/telephone V1 week 1*	Onboarding IG/ after study inclusion	Technical support call week 2	V2 Week 6*	End of study Telephone V3 week 12*	Onboarding KG/IG	Follow-up questionnaire week 24* (IG, KG)	Follow-up questionnaire week 36* (IG, KG)	Follow-up questionnaire week 48* (IG, KG)
Medical history/basic data collection	X	X									
Stress-Urge-Incontinence-questionnaire (S/U-IQ)			X				X		X	X	X
Verification of input and output Exclusion criteria	X	X									
Clarification, Declaration of consent		X									
Randomisation			X								
Questionnaires (I-QOL and ICIQ-UI-SF)			X				X		X	X	X
PGI-I							X		X	X	X
Technical support				X (IG)	X (IG)			X			
Micturition diary				X (ongoing documentation possible)		X	X	X	X	X	X
Incontinence documentation over 72h		X					X		X	X	X
Acquisition (new) Concomitant medication/therapies	X	X	X			X	X		X	X	X
Recording of adverse events**		X	X	X	X	Additional telephone enquiry	X	X	X	X	X

\*Week +/-7 d

\*\*IA/SAE/Incidentes via SZ, by telephone ([contact]) or by e-mail[[contact]](mailto:[contact]) IG:

Intervention group

KG: Control group

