## 7 Adverse events

### 7.1 Complications and risks

Muscle and joint complaints due to the physical strain are possible side effects of the therapy programme. Serious injuries should not occur due to the exclusion criteria.

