### 7.5 Product defect or device-related adverse events

The "product defect" means an inadequacy in the identification, quality, durability, reliability, safety or performance of the product, including malfunctions, application errors or inadequacy of information provided by the manufacturer and will also be reported, documented and evaluated to the sponsor.

Adverse events are documented in the eCRF by the study centre after consultation with the patient. In addition, patients are contacted by telephone once after six weeks to ask about potential SAEs and AEs.

Kranus Health GmbH\_DINKS

All AEs and SAEs are documented in the eCRF in accordance with ISO14155. SAEs must be documented and transmitted to the sponsor within 24 hours of becoming known via the eCRF system (via eCRF and automatic e-mail from the eCRF to [[contact]](mailto:[contact])). The sponsor is then obliged to assess and report the SAE in accordance with its reporting obligations.

When using the Mictera therapy programme, the risk of undesirable side effects is generally very low. A comprehensive literature search was carried out for the authorisation as a medical device and for the study protocol. No relevant risks were described when carrying out the corresponding exercises.

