## 7.6 Definition of the risk threshold

### 7.6.1 Risk threshold for patients

Patients should not have SAEs due to the use of Kranus Mictera or need to see a doctor due to this digital therapy.

For the study, a contact is made after 6 weeks within the 12-week therapy with Kranus Mictera as part of the monitoring of SAEs of study participants. If the patient reports an SAE during the course of the study, or if the patient has to see a doctor as a consequence of using Kranus Mictera, this is documented in the eCRF (including an automatic e-mail to [[contact]](mailto:[contact])) and the sponsor assesses whether there is a connection with the use of Kranus Mictera. If there is a connection with the digital therapy, will be evaluated whether further participation in the study is justifiable for the patient.

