## Kranus Health GmbH\_DINKS

- Patients for whom deviations from the study plan lead to exclusion from the PPS (drop-outs)
- Demographic data (height, age, weight, etc.)
- Other baseline characteristics
- Individual data and results for primary and secondary endpoints
- Adverse events (AE/SAE and events)

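### Table 1 schedules adverse-event recording at two contacts that only the app arm has (4 v 2 after randomisation), which could modestly raise the app arm's count in any by-arm AE summary

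*Combined protocol and SAP*

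**What the plan says.** In Table 1 (section 1.5) the row "Recording of adverse events" is marked at inclusion, V1, "Onboarding IG/ after study inclusion", the "Technical support call week 2", week 6, week 12 and all later columns. The week-6 cell differs from the rest: it reads "Additional telephone enquiry". The onboarding column belongs to the intervention group by its header. The week-2 column has no arm in its header, but the technical-support row marks it for the intervention group only, and the AE row is the only other row marked there. A footnote gives a reporting route through the study centre, by telephone or by e-mail, with no arm restriction.

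Section 7.5 says that "patients are contacted by telephone once after six weeks to ask about potential SAEs and AEs", without naming an arm. Section 7.6.1 describes what appears to be the same call differently: "a contact is made after 6 weeks within the 12-week therapy with Kranus Mictera". Section 7.1 says that "Muscle and joint complaints due to the physical strain are possible side effects of the therapy programme".

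On analysis, section 8.8 defines a safety set of all consenting patients but attaches no AE analysis to it. Section 8.10 plans tables for baseline data and for the primary and secondary endpoints only. Section 8.11 plans an individual AE listing. AEs are not among endpoints 1 to 16.

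**The concern.** In this trial, what is recorded depends largely on contact with the woman. Section 7.5 has the study centre enter AEs after speaking to her, section 6.10 plans no routine visits during the 12 weeks, and section 9.4 plans no monitoring. An additional scheduled conversation in one arm can change what is found there. The week-2 call falls early in a new exercise programme for which the protocol itself expects mild physical complaints.

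At stake is how any table of AEs by arm should be read. An excess in the app arm could partly reflect more opportunities to report. Thinner control-arm recording also weakens the background rate against which the sponsor judges relatedness (sections 7.6.1 and 7.6.2) and against which the statement of very low risk in section 7.5 would be read.

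**Working it through.** **Count of recording points (Table 1).** The plan gives no figure to reproduce. Randomisation is in the V1 column.

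- Both arms, up to and including V1: inclusion and V1 = 2.
- App arm after randomisation: onboarding, week 2, week 6, week 12 = 4.
- Control arm after randomisation: week 6, week 12 = 2, if the week-6 call includes controls; otherwise 1.
- Totals to week 12: 6 v 4.

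**Are the marks specific to contacts?** The AE row is blank at pre-screening and has its own text at week 6. The concomitant-therapy row skips both intervention-only columns, whereas the AE row includes them. Where Table 1 means continuous documentation, in the diary row, it says so. This favours a contact-specific reading without proving it.

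**Illustrative size.** The documents give neither AE rates nor detection rates, so everything in this step is assumed: equal true rates in both arms; the same chance q of detecting an AE at each scheduled contact after its onset, independently between contacts; and onboarding directly after randomisation, so that it adds almost no time at risk. The chance of detection over k remaining contacts is d(k) = 1 − (1 − q)^k.

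Remaining contacts by time of onset:

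| Onset | App arm | Control arm |
|---|---|---|
| weeks 0–2 | 3 | 2 |
| weeks 2–6 | 2 | 2 |
| weeks 6–12 | 1 | 1 |

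With onset uniform over 12 weeks:

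- App = (2/12)·d(3) + (4/12)·d(2) + (6/12)·d(1)
- Control = (6/12)·d(2) + (6/12)·d(1)

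For q = 0.3, d(1) = 0.300, d(2) = 0.510 and d(3) = 0.657. App = 0.1095 + 0.170 + 0.150 = 0.430; control = 0.255 + 0.150 = 0.405; ratio 1.06.

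With half of onset in weeks 0–2 and the rest uniform over weeks 2–12:

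- App = 0.5·d(3) + 0.5·[0.4·d(2) + 0.6·d(1)]
- Control replaces d(3) by d(2).

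For q = 0.3 this is 0.5205 / 0.447 = 1.16. With all onset in weeks 0–2 the ratio is d(3)/d(2) = 0.657/0.510 = 1.29.

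Detected-AE ratio, app to control:

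| Onset pattern | q = 0.3 | q = 0.5 | q = 0.7 |
|---|---|---|---|
| uniform | 1.06 | 1.03 | 1.01 |
| half in weeks 0–2 | 1.16 | 1.09 | 1.04 |
| all in weeks 0–2 | 1.29 | 1.17 | 1.07 |

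**If controls are not called at week 6.** With uniform onset, control detection falls to d(1) = q. The ratios become 0.430/0.3 = 1.43, 0.646/0.5 = 1.29 and 0.8155/0.7 = 1.17. The unresolved week-6 wording therefore matters more than the week-2 call.

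**After equalising.** With contacts common to both arms, the schedule is 2 v 2 after randomisation and the ratio due to scheduling is 1.00.

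**The case against.** The strongest reply is that the AE row may simply mean continuous recording. It carries no arm label, it is marked in every column from inclusion on, and either arm can report by telephone or e-mail at any time. Active asking is described only for week 6, and only the week-6 cell is worded as an enquiry. If nobody asks about AEs at the technical support call, its effect could be close to nil. This stands as a reason for the plan to say what happens at that call. It does not remove the scheduled mark, and spontaneous reporting does not replace a conversation.

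Three stronger readings are tempting, and the documents do not support them.

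- A reader might infer that a planned safety comparison is biased. None is planned: there is an AE listing, and the stopping threshold in section 7.6.2 counts product-related SAEs of like cause rather than contrasting arms.
- A reader might turn 4 v 2 into an approximate doubling of AEs. Giving each contact an equal, independent chance p of producing an AE yields 1 − (1 − p)^4 against 1 − (1 − p)^2, for example 18.5% v 9.8% at p = 5%. That ratio is built into the model: it treats onboarding as full time at risk and ignores that an event missed at week 2 can surface at week 6 or 12.
- A reader might assume that complaints cluster in the first weeks. Section 7.1 gives no timing.

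It is also fair to say that the tilt counts against the app and would not hide harm, and that closer observation of the app arm helps to test an absolute statement of low risk.

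**Conclusion.** The point holds in limited form. Scheduled AE recording after randomisation is unequal, 4 v 2, if the week-6 call covers both arms. The consequence is confined to any by-arm AE summary made from the safety set and the listing. The likely excess in the app arm is modest, a ratio of about 1.01 to 1.29, and is driven almost entirely by the week-2 call.

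That range rests on equal true rates, q between 0.3 and 0.7, and the three onset patterns shown; it is an illustration and not a bound. Spontaneous reports in both arms, or a week-2 call at which AEs are not raised, would shrink it. Fading recall of early, resolved complaints by week 6 would enlarge it. If the week-6 call leaves out controls, the count is 4 v 1 and the ratio with uniform onset is about 1.2 to 1.4.

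**What to change.** 1. **Table 1:** give the control arm the same AE question at week 2 as a short ePRO item, and state whether AEs are actively asked about at onboarding and at the week-2 call.
2. **Sections 7.5 and 7.6.1:** reconcile the two descriptions so that the week-6 enquiry explicitly applies to both arms.
3. **eCRF:** record the contact at which each AE was elicited.
4. **SAP (announced in section 8.12):** keep all AEs in the main by-arm summary and flag those first elicited at intervention-only contacts. Show a summary limited to common contacts only as a supplementary view. It should not be the main table: an app-arm event already reported at week 2 may not be repeated at week 6, so dropping it could tilt the table in the app's favour.

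Timing limits the first item. Recruitment was to end on 31.10.2024 and version 2.1 is dated 14.11.2024, exactly 14 days later, so on the printed timetable few women would still have week 2 ahead of them. For the others, the flag and the supplementary view do the work.

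Cost: one ePRO item, one eCRF field and one extra table. No data are discarded.

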## 2 List of abbreviations

AE	Adverse event
Fig.	Illustration
AK	Exclusion criteria
AWMF	Working Group of the Scientific Medical Societies
BfArM	Federal Institute for Drugs and Medical Devices
BMI	Body mass index
CCS	Complete cases
CfB	Change from baseline
d	Day - Day(s)
DiGA	Digital health application
DINKS	Digital incontinence study (study acronym)
eCRF	electronic Case Report Form
ePRO	electronic Patient-Reported-Outcomes
EK	Inclusion criteria
EMS	Electrical muscle stimulation
FAS	Full Analysis Set
FPI	First Patient In
FPO	First Patient Out
GCP	Good Clinical Practice
ICD	International Classification of Diseases
ICH-E3	Structure and Content of Clinical Study Reports E3
ICH-GCP	International Conference on Harmonisation - Good Clinical Practice Guidelines
ICIQ-SF	Incontinence Questionnaire-Urinary Incontinence Short Form
I-QOL	Incontinence quality of life questionnaire
IEF	Incontinence episode frequency

## Kranus Health GmbH\_DINKS

ISO	International Organization for Standardisation
JtR	Jump-To-Reference
AI	Confidence interval
LOCF	Last Observation Carried Forward
LPI	Last Patient In
LPO	Last Patient Out
n. a.	Not applicable
NN	Nomen nominandum
NtF	Note to File
MDR	Medical Device Regulation
MID	Minimum Important Difference
OAB	Overactive Bladder
PAM-13	Patient Activation Measure 13
PGI-I	Patient Global Impression of Improvement -Incontinence
PMR	Progressive muscle relaxation
PPS	Per protocol set
Rel-CfB	Relative Change from Baseline (CfB/Baseline)
PROM	Patient reported outcome measures
QOL	Quality of Life
SAE	Serious Adverse Event
SAP	Statistical analysis plan
SAF	Safety Set
SF	Short Form
S/U-IQ	Stress/Urge Incontinence Questionnaire
V	Visit
vs.	Versus
WoC	Withdrawal of Consent

Kranus Health GmbH\_DINKS

### 3 Test population

#### 3.1 Inclusion criteria

- ICD-10 codes:  
N39.3 Stress incontinence N39.42 Urge incontinence  
Mixed incontinence
- Persons with urge incontinence who were assigned to the female sex at birth, Stress incontinence, mixed incontinence (IE≥ 1 per day)
- Age≥ 18 years
- Mastery of the German language
- Internet access
- Tablet or smartphone access (Android not older than version 7 and iPhone not older than iPhone 9)
- Informed consent: written consent of the participating patients

#### 3.2 Exclusion criteria

**Absolute exclusion criteria that can be coded according to ICD-10 (incl. ICD-10 codes):**

- None

**Absolute exclusion criteria that cannot be coded according to ICD-10:**

- None

**Relative exclusion criteria that can be coded according to ICD-10 (incl. ICD-10 codes):**

- Acute cystitis N30.0
- Urinary bladder calculi N21.0
- Recurrent macrohaematuria that cannot be controlled conservatively R31
- Newly diagnosed bladder carcinoma < 3 months C67

**Relative exclusion criteria that cannot be coded according to ICD-10:**

- Inability to physically participate in the therapy programme
- Active pregnancy
- Botulinum toxin treatment of the urinary bladder in the last 6 months

**Study-specific methodological exclusion criteria:**

- Generally patients who are unable to understand and sign the consent form independently

## Kranus Health GmbH\_DINKS

- Newly started drug or physical therapy for micturition symptoms (anticholinergics, beta-3 receptor agonists, phytopharmaceuticals, biofeedback, EMS) in the last 4 weeks
- Severe psychiatric disorders that make it impossible to use the app
- Neurological diseases that affect the urinary tract
- Tumour and incontinence operations in the small pelvis
- Obesity per magna (BMI >35)
- Recurrent urinary tract infections N39.0 (at least 2 within 6 months or 3 infections within one year)
- Participation of the patient in another clinical trial within the last 4 weeks prior to inclusion
- addiction or other illnesses that do not allow the person concerned to assess the nature, scope and possible consequences of the clinical trial

Both groups, intervention and control group, have access to the treatment options of the regular care reality during the study period. In order to be able to evaluate the effect of the intervention in a differentiated manner, ongoing incontinence treatment (e.g. medication, interventional or surgical measures) should have been started at least four weeks before the start of the study. New therapies before the start of the study are considered an exclusion criterion.

During the study period, all newly initiated therapies for incontinence treatment (e.g. medication, interventional or surgical measures) are recorded and categorised as treatment failure. Treatment failure is also deemed to have occurred if the patient reports a deterioration in the PGI-I questionnaire at the end of the study.

The number of treatment failures is calculated and documented separately for the intervention and control groups.

Patients in the control group are not given access to the app-based intervention during the twelve-week study period. After completion of the survey at the end of the study (week 12, see 1.5. Visit schedule), they are free to use the app-based therapy.

Kranus Health GmbH\_DINKS

## 4 Question and background

Urinary incontinence in women is a very common, often under-diagnosed and taboo condition, the main symptom of which is uncontrolled urine loss. This is accompanied by a significant reduction in quality of life and considerable suffering. Incontinence complaints are divided into stress incontinence, urge incontinence and mixed urinary incontinence.

### 4.1 Forms of urinary incontinence

#### 4.1.1 Stress incontinence

Stress with an increase in intra-abdominal pressure (lifting, coughing, sneezing, laughing, jumping, etc.) leads to involuntary loss of urine, which is known as stress incontinence. One of the causes is a decrease in tone or pre-damaged pelvic floor muscles, for example after pregnancy and childbirth or in old age as a result of sarcopenia and decreasing muscle strength.

The severity of stress incontinence is determined by the intensity of the stress:

*Grade 1: Leakage of urine when coughing, sneezing, pressing, lifting, carrying heavy objects.*

*Grade 2: Urine leakage when walking or standing up.*

*Grade 3: Urine leakage even when lying down.*

#### 4.1.2 Urge incontinence

Urge incontinence is when there is an involuntary loss of urine combined with a sudden urge to urinate (imperative urge to urinate). This is caused by involuntary spontaneous contractions of the detrusor of the bladder (detrusor hyperactivity, OAB overactive bladder).

#### 4.1.3 Mixed incontinence

Mixed incontinence is when there involuntary loss of urine during physical exertion on the one hand and an imperative urge to urinate in the sense of urge incontinence on the other. In most cases, one of the components predominates.

### 4.2 Distribution and frequency

According to clinical studies, the distribution is as follows: Stress incontinence (50%), urge incontinence (14%), mixed form (32%) [10].

In Germany, around 15-25% of women are affected by various forms of urinary incontinence [1]. The frequency increases age. A high number of unreported cases can be assumed [2].

### 4.3 Diagnosis of urinary incontinence

The diagnostic recommendations for urinary incontinence in the German S2 guidelines are based on expert opinion and clinical studies [2]. The diagnostic steps are outlined below:

A detailed **medical history** enables incontinence to be categorised in the majority of cases [11]. In addition to the obstetric and gynaecological history, concomitant illnesses and medication are also relevant. The patient's individual impairment and level of suffering should also be enquired about.

The general **clinical examination** serves to rule out high residual urine volumes, resistance or masses in the pelvis. The gynaecological examination can be used to assess possible diseases of the external genitalia and a prolapse of the internal genitalia (descensus, prolapse). Palpation of the pelvic floor muscles enables an assessment of their contractility.

The use of validated **questionnaires** is recommended in guidelines. The severity of the disease, type of incontinence and disease-related quality of life can be recorded.

The **micturition diary** is used to quantify symptoms and record the frequency of incontinence episodes. It also enables the measurement of micturition volumes and the determination of the 24-hour total urine volume or the nocturnal urine volume. The use of the micturition diary is strongly recommended in the guidelines for all forms of incontinence [2]. To increase the accuracy of the results, the use of a three-day micturition diary is used to determine a 24-hour average [12].

The **pad test** quantifies urine loss by wearing pads during documented physical activity and weighing them after a set period of time. Both the 1-hour pad test and the 24-hour pad test exist. Although the 24-hour test is more precisely reproducible, the standardisation of physical activities is more complex [13].

It is important to know if there is **residual urine** before initiating treatment for incontinence, as drug therapy options such as anticholinergics can impair bladder emptying. The amount of residual urine is determined by ultrasound examination. However, studies on the determination of residual urine in women are rare and there is no standard definition for a pathological amount of residual urine. In women with stress incontinence, only 16% had residual urine > 100 ml [14].

**Urodynamics** with bladder manometry, uroflowmetry and urethral pressure profile are used to assess the bladder during the filling and emptying phase. Routine use of this examination prior to conservative treatment of uncomplicated stress incontinence and untreated overactive bladder is not recommended in the guidelines [2].

Of the **imaging procedures**, sonography plays an important role in determining residual urine (see above). Transcavitary functional sonographic procedures are only relevant in the context of surgical treatment of incontinence.

To summarise, it can be stated that, of the diagnostic procedures described, only questionnaires and pad tests for the quantitative assessment of the

Kranus Health GmbH\_DINKS

incontinence and to test the effectiveness of therapy. However, the use of the various validated questionnaires is heterogeneous [4].

## 4.4 Treatment of urinary incontinence

In the clinical practice of incontinence treatment, **conservative therapies** (less invasive, reversibility) are generally used before surgical therapies. For all types of incontinence, pelvic floor muscle training, cognitive behavioural therapy, lifestyle changes and self-management therapies are successful and represent an alternative to drug therapies [15]. For this reason, both the German AWMF guidelines [2] and the European guidelines for urology (EAU guidelines) recommend these measures with strong scientific evidence [3].

